4.6.3. Narratives

The following are “notable” events, from start of study intervention through end of study participation (or data cutoff for the submission if earlier):

- deaths
- serious AEs
- other AEs judged to be of clinical importance by Lilly, and
- permanent discontinuations of study intervention due to AEs.

Narratives (patient-level data and summary paragraph) will be provided for participants in the safety population with at least 1 notable event.

Safety topics of interest are not considered notable events, unless 1 of the above criteria is met. Displays with individual participant-level data will be created for safety topics of interest using various formats such as a customized listing and/or a customized graphical patient profile as specified in the section associated with the safety topic of interest. Medical case summaries or vignettes will be provided if deemed relevant for the discussion of the safety topic of interest.

4.6.4. Device Product Complaints (if applicable)

The ISA-SAP will identify whether a listing for device product complaints is necessary. The listing will include, as a minimum, the device product complaint that led to an AE or that could have led to a serious AE had intervention not been taken.

4.6.5. Additional Safety Assessments

Sections 4.6.5.1 through 4.6.5.5 specify additional safety analyses for all ISAs for clinical laboratory evaluations, vital signs, hepatic safety, infections, and malignancy. Section 4.6.5 of the ISA-SAP may clarify these analyses or specify additional analyses of interest.

4.6.5.1. Clinical Laboratory Evaluations

Summaries will be created for the laboratory analyte measurements as noted in [Table 6.3](#). The planned summaries are provided in [Table 4.3](#).

Baseline and postbaseline values are defined as follows:

- **last baseline:** the last nonmissing observation in the baseline period; unplanned measurements will be excluded
- **last postbaseline:** last nonmissing observation in the postbaseline period; unplanned measurements will be excluded
- **maximum baseline:** maximum nonmissing value during the baseline period; planned and unplanned measurements will be included

- **maximum postbaseline:** maximum nonmissing observation during the postbaseline period; planned and unplanned measurements will be included
- **minimum baseline:** minimum nonmissing value during the baseline period; planned and unplanned measurements will be included, and
- **minimum postbaseline:** minimum nonmissing observation during the postbaseline period; planned and unplanned measurements will be included.

Box plots evaluate trends over time and assess the potential impact of outliers on central tendency summaries. Summaries and analyses of minimum and maximum values are used to identify laboratory analytes that have an imbalance in the most extreme values and extreme changes, which would indicate further investigation is required.

Table 4.3.**Tables and Figures for Clinical Laboratory Evaluations**

Analysis Type	Analysis Details	Sample
Box plots and mean/SD plots for observed values by visit	
Includes participants who have both a baseline and at least 1 postbaseline measurement from a planned visit.
 
Unplanned measurements will be excluded.
 
Last baseline will be used.
 
Original-scale data will be used.
 
Both SI and conventional units will be provided in the axis within a single plot.
 
No inferential statistics.
	Overall Analysis
Box plots and mean/SD plots for change from baseline values by visit	
Includes participants who have both a baseline and at least 1 postbaseline measurement from a planned visit.
 
Unplanned measurements will be excluded.
 
Last baseline will be used.
 
No inferential statistics.
	Overall Analysis
Participants with elevated or low values meeting specified levels	
Excludes analytes collected qualitatively.
 
Definitions of low and high values in Tables 59 and 60 from FDA's Standard Safety Tables and Figures Integrated Guide will be used for the numerator^a.
 
Includes participants with at least 1 postbaseline measurement.
 
Maximum baseline is used for elevated assessments and minimum baseline is used for low assessments.
 
See Table 24 from FDA's Standard Safety Tables and Figures Integrated Guide^a.
	Overall Analysis
Listing of abnormal laboratory findings	
Includes laboratory analytes collected quantitatively (high or low during postbaseline using Level 2 definitions; see FDA's Standard Safety Tables and Figures Integrated Guide^a) and qualitatively (abnormal during postbaseline).
 
Includes participant identification, treatment group, laboratory analyte collection day (that is, days from start of study intervention), analyte name, and analyte finding.
	Overall Analysis

Abbreviations: SD = standard deviation; SI = international system of units.

^a CDER/BIRRS 2022.

Scatter plots to support clinical laboratory evaluations

Scatter plots of maximum-by-maximum measurements and minimum-by-minimum measurements will not be created a priori. They may be created if warranted after review of the planned tables and figures, using Figures 6.3 and 6.4 from the Analysis and Displays for Labs white paper (PHUSE 2022) as the model. Analysis Data Model datasets will include variables to enable the creation of scatter plots for use in either an interactive tool or for ad hoc figures.

4.6.5.2. Vital Signs, Physical Findings, and Other Observations Related to Safety

The definitions for last/maximum/minimum baseline/postbaseline provided in Section 4.6.5.1 also apply to this section.

The planned summaries are provided in [Table 4.4](#). The measurements analyzed for vital signs and physical characteristics include systolic blood pressure, diastolic blood pressure, pulse, weight, and temperature.

Table 4.4. Tables and Figures for Vital Signs and Physical Characteristics

Analysis Type	Analysis Details	Sample
Box plots and Mean/SD plots for observed values by visit	Includes participants who have both a baseline and at least 1 postbaseline measurement from a planned visit. Unplanned measurements will be excluded. Last baseline will be used. No inferential statistics.	Overall Analysis
Box plots and Mean/SD plots for change from baseline values by visit	Includes participants who have both a baseline and at least 1 postbaseline planned measurement. Unplanned measurements will be excluded. Last baseline will be used. No inferential statistics.	Overall Analysis
Participants with elevated or low values meeting specified levels, vital signs	Definitions provided in Tables 31-33 from FDA's September 2022 Standard Safety Tables and Figures Integrated Guide will be used for the numerator ^a . Includes participants with at least 1 postbaseline measurement.	Overall Analysis

Abbreviations: SD = standard deviation.

^a CDER/BIRRS 2022.

Scatter plots to support vital sign evaluations

Scatter plots of maximum-by-maximum measurements and minimum-by-minimum measurements will not be created a priori. They may be created if warranted after review of the planned tables and figures, using Figures 6.3 and 6.4 from the Analysis and Displays for Labs white paper (PHUSE 2022) as the model. Analysis Data Model datasets will include variables to enable the creation of scatter plots for use in either an interactive tool or for ad hoc figures.

4.6.5.3. Hepatic Safety

Hepatic labs include alanine aminotransferase, aspartate aminotransferase, total bilirubin, direct bilirubin, serum alkaline phosphatase, international normalized ratio, and gamma-glutamyltransferase. When criteria are met for hepatic evaluations, investigators will conduct close monitoring of hepatic symptoms and liver tests, perform a comprehensive evaluation for alternative causes of abnormal liver tests, and complete follow-up hepatic safety eCRFs.

[Table 4.5](#) describes the planned summary tables related to hepatic safety.

Table 4.5. Summary Tables and Figures Related to Hepatic Safety

Analysis	Sample
Abnormal Postbaseline Categories – Hepatic Safety Parameters 
 ALT: The number and percentage of participants with a measurement greater than or equal to 1 time (1X), 3 times (3X), 5 times (5X), 10 times (10X), and 20 times (20X) the performing lab ULN during the treatment period for all participants with a postbaseline value. AST: The number and percentage of participants with a measurement greater than or equal to 1 time (1X), 3 times (3X), 5 times (5X), 10 times (10X), and 20 times (20X) the performing lab ULN during the treatment period for all participants with a postbaseline value. ALP: The number and percentage of participants with a measurement greater than or equal to 2 times (2X), and 3 times (3X) the performing lab ULN during the treatment period will be summarized for all participants with a postbaseline. TBL: The number and percentage of participants with a measurement greater than or equal to 2 times (2X), 5 times (5X), and 8 times (8X) the performing lab ULN during the treatment period will be summarized for all participants with a postbaseline value. DBL: The number and percentage of participants with a measurement greater than or equal to 2 times (2X) and 5 times (5X) the performing lab ULN during the treatment period will be summarized for all participants with a postbaseline value. GGT: The number and percentage of participants with a measurement greater than or equal to 2 times (2X) the performing lab ULN during the treatment period will be summarized for all participants with a postbaseline value. 	Overall Analysis
Hepatocellular Drug-Induced Liver Injury Screening Plot (TBL vs. ALT or AST)	Overall Analysis
Cholestatic Drug-Induced Liver Injury Screening Plot (TBL vs. ALP)	Overall Analysis

Abbreviations: ALP = alkaline phosphatase; ALT = alanine transaminase; AST = aspartate aminotransferase; DBL = direct bilirubin; GGT = gamma-glutamyltransferase; TBL = total bilirubin; ULN = upper limit of normal.

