The blinded CCI [REDACTED] week maintenance treatment period begins CCI [REDACTED]

CCI [REDACTED] Participants having at least an CCI [REDACTED] response at Week 16 will receive a maintenance dosing regimen, also CCI [REDACTED] as listed here.

Week 16 responders who were originally randomized to this induction regimen...	Will receive this maintenance regimen:
LY3454738 CCI mg CCI	by rerandomization in CCI ratio: LY3454738 CCI mg CCI or placebo
LY3454738 CCI mg CCI	LY3454738 CCI mg CCI
LY3454738 CCI mg CCI	LY3454738 CCI mg CCI
placebo	placebo CCI

The maintenance period includes an “escape arm” for participants whose EASI response suggests the need for a higher dose. The escape therapy is LY3454738 CCI mg CCI [REDACTED] A participant will receive this escape therapy under the conditions listed here.

Begin LY3454738 CCI mg CCI as escape therapy...	if the participant...
At Week 16	has not achieved an CCI [REDACTED] response at Week 16.
At Weeks CCI [REDACTED]	has not achieved an CCI [REDACTED] response at Weeks CCI [REDACTED]

A participant receiving escape therapy will continue receiving escape therapy through the last dosing visit of the study (Week CCI [REDACTED] unless the participant is discontinued from study intervention.

Topical rescue medication is permitted (not required) in the induction period from Week 8 until Week 16 for participants who do not achieve an CCI [REDACTED] response. In the maintenance period, use of topical rescue medication is permitted (not required) from Week CCI [REDACTED] until the end of the study for participants who do not achieve an CCI [REDACTED] response. Participants who receive at least 2 doses of escape therapy at 2 consecutive visits will be permanently discontinued from study intervention if they fail to achieve an CCI [REDACTED] response.

This study design includes investigator and participant blinding (masking). An internal assessment committee (IAC) will exist for the purpose of reviewing safety data in an unblinded fashion.

In summary, Study FR01 includes 4 study periods over a total study duration of approximately CCI weeks:

- Screening: from CCI days prior to randomization at Week 0 (Study Day 1)
- Treatment Period – Induction: from randomization at Week 0 (Study Day 1) through assessments at Week 16
- Treatment Period – Maintenance: from dose administration at Week 16 CCI CCI and
- Posttreatment Follow-Up: 2 visits, the last visit being CCI after randomization CCI

Brief Summary:

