Asthma Control Questionnaire-5 (ACQ-5)						X					X	
Clinician-administered assessments (electronic)												
vIGA-AD	X	X	X	X	X	X	X	X	X	X	X	
Eczema Area and Severity Index (EASI)	X	X	X	X	X	X	X	X	X	X	X	
SCORing Atopic Dermatitis (objective) (SCORAD)	X	X	X	X	X	X	X	X	X	X	X	
Fitzpatrick Scale of Skin Phototypes												Not performed in these study periods.
Clinician-administered assessments (paper)												
Columbia-Suicide Severity Rating Scale (C-SSRS) Since Last Assessed	X	X	X	X	X	X	X	X	X	X	X	AE collection should occur prior to collection of the C-SSRS. Adapted for the assessment of ideation and behavior categories only.
Participant diary (electronic)												
CCI												

Table 2. Activities for maintenance and posttreatment follow-up periods, early discontinuation visit, and unscheduled visit (Study J4E-MC-FR01).
 Note: The posttreatment follow-up visits are required for all randomized participants.

Week	CCI											Comment
Study day												Study Day 1 is day of first dose.
Visit interval tolerance (window) in days	±3	±3	±3	±3	±3	±3	±3	—	—	±7	±7	
CRF visit number	CCI							ED	—	V808	V812	
CCI												
Diary review	X	X	X	X	X	X	X	X	X	X	X	Diary contains the following assessments: CCI Atopic Dermatitis Sleep Scale (ADSS), and Skin Pain Numeric Rating Scale (Skin Pain NRS).
Diary return								X			X	
Participant education												
CCI												
Diary education												Education can be provided as needed at any time.

Table 2. Activities for maintenance and posttreatment follow-up periods, early discontinuation visit, and unscheduled visit (Study J4E-MC-FR01).
 Note: The posttreatment follow-up visits are required for all randomized participants.

Week	CCI											Comment
Study day												Study Day 1 is day of first dose.
Visit interval tolerance (window) in days	±3	±3	±3	±3	±3	±3	±3	—	—	±7	±7	
CRF visit number	CCI							ED	—	V808	V812	
Laboratory tests and sample collections												Collect before dosing unless otherwise specified.
Hematology			X			X		X		X	X	
Clinical chemistry			X			X		X		X	X	
Urine or serum pregnancy test (local)	X	X	X	X	X	X	X			X	X	For WOCBP, a pregnancy test must be performed, with the result available within 24 hours prior to dosing (see Section 8.2.7 of this ISA and Section 8.2.7 of the master IMMB protocol). Additional pregnancy tests should be performed at any time if a menstrual period is missed, or there is clinical suspicion of pregnancy, or as required by local law or regulation.

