Urinalysis						X		X			X	
Estimated glomerular filtration rate (eGFR)						X		X				Calculated using Chronic Kidney Disease Epidemiology Collaboration (CKD-EPI) Creatinine Equation (2021).

Table 2. Activities for maintenance and posttreatment follow-up periods, early discontinuation visit, and unscheduled visit (Study J4E-MC-FR01).
 Note: The posttreatment follow-up visits are required for all randomized participants.

Week	CCI											Comment
Study day												Study Day 1 is day of first dose.
Visit interval tolerance (window) in days	±3	±3	±3	±3	±3	±3	±3	—	—	±7	±7	
CRF visit number	CCI							ED	—	V808	V812	
Hepatitis B virus (HBV) DNA		X				X			X		X	Only for participants who are anti-HBc positive at Visit 401 (see Section 8.2.9 of the master IMMB protocol).

Table 2. Activities for maintenance and posttreatment follow-up periods, early discontinuation visit, and unscheduled visit (Study J4E-MC-FR01).
 Note: The posttreatment follow-up visits are required for all randomized participants.

Week	CCI											Comment
Study day												Study Day 1 is day of first dose.
Visit interval tolerance (window) in days	±3	±3	±3	±3	±3	±3	±3	—	—	±7	±7	
CRF visit number	CCI							ED	—	V808	V812	
Immunogenicity (ADA) samples			X			X		X			X	On dosing visits, collect samples before dosing. Collect additional samples at specified times relative to onset of CCI events (see Section 8.3.1.1 and Attachment 1, Section 10.1.2).
Stored samples												
Genetics sample												Sample can be obtained at or after Study Day 1.
CCI												
Randomization and dosing-related activities												
Register visit with IWRS	X	X	X	X	X	X	X	X		X	X	
Dispense study intervention via IWRS	X	X	X	X	X	X						The last dose is given at Week 40.

Table 2. Activities for maintenance and posttreatment follow-up periods, early discontinuation visit, and unscheduled visit (Study J4E-MC-FR01).
 Note: The posttreatment follow-up visits are required for all randomized participants.

Week	CCI										Comment
Study day											Study Day 1 is day of first dose.
Visit interval tolerance (window) in days	±3	±3	±3	±3	±3	±3	±3	—	—	±7	±7
CRF visit number	CCI					ED	—	V808	V812		
Administer study intervention	X	X	X	X	X	X					The last dose is given at Week CCI

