For induction period safety analyses, the baseline period is defined as the time from Visit 401 to the first dose of study intervention. For the safety analyses during the maintenance period, baseline is defined as the last available value before the first dose of study intervention during the maintenance period. In most cases, this will be the measure recorded at Week 16. For the safety analyses during the posttreatment follow-up period, baseline is defined as the last nonmissing assessment on or prior to entering the posttreatment period, that is, on or prior to Week 44 or ED visit.

Missing data

For the estimand defined in Section 3.1, missing data after accounting for ICEs is expected to be uncommon. Thus, the handling of any missing data remaining after accounting for ICEs will be specified in the ISA-SAP. Missing data imputation methods for supplementary estimands will be described in the ISA-SAP.

Induction treatment comparisons

For binary efficacy and PROs, CCI [REDACTED]

CCI
CCI

[REDACTED]

[REDACTED]

[REDACTED]

For continuous efficacy and patient-reported outcomes, CCI [REDACTED]

CCI
CCI

[REDACTED]

[REDACTED]

Maintenance treatment comparisons

The efficacy of different maintenance regimens will primarily be assessed with descriptive statistics across the maintenance period. Frequencies and percentages will summarize binary outcomes, and means and standard deviations will summarize continuous outcomes. The ISA-SAP may include additional exploratory analyses for maintenance efficacy, including, but not limited to, inferential efficacy analyses and the efficacy of different maintenance regimens across differing levels of response at induction, for example, CCI [REDACTED] EASI-75 responders at Week 16.

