4.6.5.2. Vital Signs, Physical Findings, and Other Observations Related to Safety	21
4.6.5.3. Hepatic Safety	22
4.6.5.4. Infections	22
4.6.5.5. Malignancy	24
4.7. Other Analyses.....	24
4.7.1. Subgroup Analyses	24
4.8. Interim Analyses.....	24
CCI [REDACTED]	25
4.9. Changes to Protocol-Planned Analyses	25
5. Sample Size Determination	26
6. Supporting Documentation	27
6.1. Appendix 1: Demographic and Baseline Characteristics	27
6.2. Appendix 2: Definition of Efficacy Endpoints and Patient- Reported Health Outcomes.....	28
6.3. Appendix 3: Laboratory Analytes for Safety Analyses	31
7. References.....	32

Table of Contents

Table		Page
Table 1.1. SAP Version History Summary	4	
Table 3.1. The Minimum Analysis Sets for the ADMP.....	9	
Table 4.1. Baseline and Postbaseline Period Definitions for Overall and Induction Safety Analyses.....	14	
Table 4.2. Tables and Listings Related to Adverse Events.....	17	
Table 4.3. Tables and Figures for Clinical Laboratory Evaluations	20	
Table 4.4. Tables and Figures for Vital Signs and Physical Characteristics.....	21	
Table 4.5. Summary Tables and Figures Related to Hepatic Safety.....	22	
Table 4.6. Summary Tables, Figures, and Listings Related to Infection Safety	24	
Table 6.1. Demographic and Baseline Characteristic Variables.....	27	
Table 6.2. Derivation of Efficacy and Patient-Reported Health Outcomes	28	
Table 6.3. Laboratory Analytes.....	31	

Version History

This Statistical Analysis Plan for Study J4E-MC-IMMB is based on the protocol dated 13MAR2023.

Table 1.1. SAP Version History Summary

SAP Version	Approval Date	Change	Rationale
1	See date on Page 1	Not Applicable	Original version

1. Introduction

The purpose of this Statistical Analysis Plan (SAP) is to describe and specify the analyses relevant across the different intervention specific appendices (ISAs) of the atopic dermatitis master protocol (ADMP). The ADMP-specific SAP (MP-SAP) will specify

1. baseline characteristics of interest
2. safety analyses common across ISAs
 - a. overall safety including the posttreatment follow-up period, which accounts for safety events after dosing stops but drug has not washed out, and
 - b. safety during the induction treatment period, which is common to all ISAs, and
3. analysis framework for borrowing placebo data in the ADMP.

There are no changes to the analyses described in Protocol J4E-MC-IMMB (IMMB).

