4.4. Secondary Endpoints/Estimands Analysis

The MP-SAP will focus on two safety analyses: (1) overall safety profile across treatment periods including posttreatment follow-up, and (2) safety profile during induction. The ISA-SAP will define the treatment groups, if relevant, for the overall and induction safety analyses.

Please see Section 4.4 of the relevant ISA-SAP for secondary endpoints and/or estimands for efficacy analyses or ISA-specific safety analyses.

Estimand for overall safety analyses

A secondary clinical question of interest is: what is the difference between active study intervention versus placebo in the number, percent, and/or incidence rates (IRs) of treatment-emergent adverse events (TEAEs) of interest?

The estimand is described by the following attributes:

- Population: participants with moderate-to-severe AD
- Endpoint(s): number, percent, and/or IRs for first TEAEs of interest
- How to account for intercurrent events:
 - Early Permanent Discontinuation of Study Intervention: TEAEs during the posttreatment follow-up will be considered attributable to the study intervention
 - Use of Prohibited or Rescue Medication: TEAEs after the use of prohibited or rescue medication will be considered attributable to the study intervention.

- Assignment to Escape Arm (if applicable): if a participant escapes from placebo to active study intervention, subsequent TEAEs will be attributable to the active study intervention, and
- Assignment to Placebo Withdrawal Arm (if applicable): if a participant is re-randomized from active study intervention to placebo, TEAEs will be considered attributable to the active study intervention until the completion of the study
- Population-level summary: the difference in IRs for TEAEs of interest between participants receiving (rather than assigned to) active study intervention versus placebo, and
- Rationale for estimand:
 - TEAEs of interest for participants receiving active study intervention are considered attributable to study intervention

CCI

- the use of prohibited or rescue medication are potential components of treatment regimens and should therefore be attributable to study intervention.

Secondary estimand for safety during induction period

A secondary clinical question of interest is: what is the difference between the active study intervention versus placebo (or active comparator) in the number, percent, and/or IRs of TEAEs of interest during the induction treatment period?

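### SAP Table 4.5 limits its hepatic counts to the treatment period, although it is labelled an Overall Analysis, which includes posttreatment follow-up

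*SAP*

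**What the plan says.** The first row of SAP Table 4.5 is titled as abnormal postbaseline categories, and its Sample column reads Overall Analysis. For ALT and AST it counts participants at or above stated multiples of "the performing lab ULN during the treatment period for all participants with a postbaseline value". The ALP, total bilirubin, direct bilirubin and GGT rules restrict the count in the same way. The other two rows are liver-injury plots, also Overall Analysis. The first is the "Hepatocellular Drug-Induced Liver Injury Screening Plot (TBL vs. ALT or AST"), and neither plot mentions a treatment period.

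The SAP introduction describes the overall analysis as "overall safety including the posttreatment follow-up period, which accounts for safety events after dosing stops but drug has not washed out". SAP Section 4.4 describes it as the "overall safety profile across treatment periods including posttreatment follow-up". In Table 4.1, the overall postbaseline window for laboratory tests ends at the earliest of ISA discontinuation, ISA completion or database cut-off. For participants initially on placebo, the first escape dose is a further end point. The end of treatment is not an end point for anyone.

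The SAP does not define treatment period. The Protocol synopsis lists two treatment periods, induction and maintenance, and then, as a separate item, "Posttreatment Follow-Up: 2 visits, the last visit being" a redacted time after randomization.

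**The concern.** The label and the counting rule point to different windows. If a programmer follows the rule as written, a hepatic elevation first seen at a follow-up visit does not enter the Table 4.5 count. The SAP gives covering the time before the drug has washed out as the reason for an overall analysis. If another programmer follows the label and Table 4.1, the same value is counted. Two correct-looking programs could therefore produce different hepatic tables.

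Within the literal rule, numerator and denominator also differ. A participant whose only postbaseline values come from follow-up enters the denominator but can never enter the numerator. The same participant could appear in a liver-injury plot and be absent from the counts above it.

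**Working it through.** The plan gives no figure to reproduce. The check is a comparison of windows and a count of scheduled draws.

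**Where follow-up falls.** SoA Table 2 states "The last dose is given at Week 40". Protocol Section 4.1 places the follow-up visits about 8 and 12 weeks after the last dosing visit: 40 + 8 = Week 48 and 40 + 12 = Week 52. Protocol Section 9.3.1 takes the baseline for follow-up safety from the last assessment "on or prior to entering the posttreatment period, that is, on or prior to Week 44 or ED visit". Both visits lie after Week 44, so in the protocol's terms they are posttreatment.

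**Windows side by side.**

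| Item in Table 4.5 | Window as written |
|---|---|
| Row label (Overall Analysis) | first dose to ISA discontinuation, ISA completion or cut-off (Table 4.1) |
| Numerator, all six rules | treatment period, not defined |
| Denominator | any postbaseline value |
| Two liver-injury plots | no limit beyond Overall Analysis |

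Elsewhere, in Section 4.6.5.1, the SAP takes maximum and minimum laboratory values over the postbaseline period. Table 4.5 is the place where the wording changes.

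**Scheduled chemistry draws (SoA Tables 1 and 2).**

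- Table 1 has 5 marks: 1 at Week 0 and 4 later in induction.
- Table 2 has 5 marks: 2 in maintenance, 1 at the early discontinuation visit, and 1 each at V808 and V812.
- Completer (no early discontinuation visit): 4 + 2 + 2 = 8 postbaseline draws. Literal rule: 4 + 2 = 6. Omitted: 2 of 8, or 25%.
- Placebo participant who escapes at Week 16 and then completes: Table 4.1 starts the active window at the first escape dose. The schedule's instruction is "Collect before dosing unless otherwise specified", so the Week 16 sample precedes that dose. Draws in the active window: 2 + 2 = 4. Literal rule: 2. Omitted: 2 of 4, or 50%.
- Active-arm participant who escapes at Week 16 and then completes: the window still starts at the first active dose, so the count is 8 against 6, as for a completer.

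**The case against.** The strongest reply is that the surrounding text already settles the meaning. The row title, the denominator and the Sample label all say postbaseline or overall, and Table 4.1 defines that window. Section 4.4 speaks of treatment periods as including follow-up, so the SAP's own usage can place follow-up inside the phrase. The narrow meaning comes from the FR01 protocol, whereas this SAP serves every ISA under the master protocol. Protocol Section 9.3.5 refers safety analyses to that master protocol, and SAP Section 4.6.5 lets the ISA-SAP clarify. Neither document is available here.

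Much of this stands. The broader reading may well be the intended one, and the cause may be loose drafting. It does not remove the problem, because the operative counting rule still names a narrower period six times and the visible text does not say which reading governs.

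Three stronger inferences are tempting, and the documents do not support them:

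- *Follow-up liver elevations would go unreported.* They would not. The Table 4.3 displays are Overall Analysis, and Table 6.3 lists ALT, AST, ALP and bilirubin among their analytes, so follow-up values remain covered under those displays' own thresholds. GGT and separately reported direct bilirubin are not listed in Table 6.3. The liver-injury plots also remain.
- *V808 and V812 hold the only scheduled chemistry draws after the last dose.* This depends on whether the last maintenance mark sits at the last dosing visit. The week headers are redacted and the column positions in the schedule text are not reliable. In Table 1 the last chemistry mark falls one column before the Week 16 column, yet Protocol Section 10.5 expects chemistry at Week 16. The count of 2 in 8 does not depend on this.
- *All escapers lose half their draws.* Only those escaping from placebo do, because Table 4.1 resets the window only for them. About 68 of about 260 participants are planned for placebo, and only some will escape.

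**Conclusion.** The inconsistency holds. Table 4.5 is an overall analysis by label and denominator, but its six numerators are limited to an undefined treatment period. On the protocol's use of that term, the limit removes both follow-up draws: 2 of 8 for a completer and 2 of 4 for a placebo participant escaping at Week 16. Because Section 4.4 permits the other reading, the finding is that the text supports two counts, not that follow-up data will certainly be excluded.

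The number of participants affected cannot be derived from the documents, which give no laboratory distributions or event rates. The consequence is limited to descriptive hepatic counts: SAP Section 4.6 includes no p-values for safety unless the ISA-SAP specifies them. Nothing here bears on the primary endpoint or power, and no bias in the randomized comparison is shown. Severity is minor. Confidence is moderate, since the master protocol and the ISA-SAP may resolve the wording. The draw counts assume that all scheduled visits are attended and no unscheduled tests are added.

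**What to change.** In all six analyte rules of Table 4.5, replace the treatment-period wording with a reference to the postbaseline period defined in Table 4.1. Numerator, denominator and plots then share one window. If follow-up is meant to be excluded, define treatment period, state the exclusion, and do not label those counts Overall Analysis. If the master protocol or ISA-SAP already settles the matter, a cross-reference in Table 4.5 is enough.

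The cost is a few words in one table, with no new data. Because this is the master SAP, one edit serves every ISA.
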